8.2 Background Characteristics

8.2.1 Subject Disposition

The number of subjects in the following categories will be summarized by treatment groups (IVA 150 mg q12h, VX-561 25 mg qd, VX-561 50 mg qd, VX-561 150 mg qd, VX-561 250 mg qd), VX-561 total (pooling all VX-561 arms) and overall (pooling all 5 arms):

- All Subjects Set
- Full Analysis Set
- Safety Set
- Randomized
- Randomized but not dosed in the Treatment Period

The number and percentage (based on FAS) of subjects in each of the following disposition categories will be summarized:

- Completed study drug treatment
- Prematurely discontinued treatment and the reason for discontinuation
- Completed study (i.e., completed Safety Follow-up Visit)
- Prematurely discontinued the study and the reason for discontinuation

A listing will be provided for subjects who discontinued treatment or who discontinued study with reasons for discontinuation.

8.2.2 Demographics and Baseline Characteristics

Demographics, medical history and baseline characteristics will be summarized based on the FAS, and presented by treatment groups, VX-561 total and overall.

Demographic data will include the following:

- Age at baseline (in years)
- Sex (female or male)
- Ethnicity (Hispanic or Latino, not Hispanic or Latino, and not collected per local regulations)
- Race (White, Black or African American, Asian, American Indian or Alaska Native, Native Hawaiian or Other Pacific Islander, Other, and not collected per local regulations)

Baseline characteristics will include the following:

- Weight (kg)
- Height (cm)
- BMI (kg/m²)

Stratification categories will include the following:

- ppFEV₁ at the Screening Visit (<70, ≥70)

Disease characteristics will include the following:

- ppFEV₁ at baseline (<40, ≥ 40 to <70, ≥70 to ≤100, >100)
- ppFEV₁ at baseline (continuous)
- Sweat Chloride at baseline (continuous)
- Prior use of dornase alfa (Yes, No)
- Prior use of azithromycin (Yes, No)
- Prior use of inhaled antibiotic (Yes, No)
- Prior use of any bronchodilator (Yes, No)
- Prior use of any inhaled bronchodilator (Yes, No)

- Prior use of any inhaled hypertonic saline (Yes, No)
- Prior use of any inhaled corticosteroids (Yes, No)
- Infection with *Pseudomonas aeruginosa* with 2 years prior to screening (Positive, Negative)

In addition, number (%) of subjects (based on the FAS) will be summarized by genotype category (*F508del/Gating*, *Gating/Gating* and *Gating/Other*) in a total column.

Data listings will also be provided for:

- Informed consent;
- Inclusion/Exclusion criteria violation for subjects with any such violations.

8.2.3 Medical History

Medical history will be coded by using the Medical Dictionary for Regulatory Activities (MedDRA). For the FAS, medical history will be summarized descriptively by system organ class and preferred term. The corresponding data listing will also be provided.

8.2.4 Prior and Concomitant Medications

Medications will be coded using the World Health Organization Drug Dictionary Enhanced (WHODD, version March 2019, format B3 or the most updated version) and categorized as follows:

Prior medication: any medication that started before the date of first dose of study drug.

Concomitant medication: medication continued or newly received during the TE Period.

Post-treatment medication: medication continued or newly received after the TE period.

A given medication may be classified as a prior, concomitant medication, or post-treatment medication; both prior and concomitant; both concomitant and post-treatment; or prior, concomitant, and post-treatment. If a medication has a missing or partially missing start/end date or time and if it cannot be determined whether it was taken before the first dose of study drug, concomitantly during the TE Period, or after the TE Period, it will be considered in all 3 categories of prior, concomitant, and post-treatment medication.

Prior medications and concomitant medications will be summarized descriptively using frequency tables by Preferred Name based on the FAS, and presented by treatment groups, VX-561 total and overall.

All medications (including post-treatment medications) will be provided in an individual subject data listing. Details for imputing missing or partial start and/or stop dates of medication are described in [Appendix B](#).

8.2.5 Study Drug Exposure

Study drug exposure (in days) will be calculated as: last dose date of study drug – first dose date of study drug + 1 day, regardless of study drug interruption. Exposure will be summarized descriptively by the number of subjects (n), mean, SD, median, min, and max. It will also be

summarized in categories: ≤ 4 weeks, >4 to ≤ 8 weeks, >8 to ≤ 12 weeks, and >12 weeks, using counts and percentages.

Exposure summaries will be based on the Safety Set, and presented by treatment groups.

8.2.6 Study Drug Compliance

Study drug compliance will be calculated as: $100 \times [1 - (\text{total number of days of study drug interruption}) / (\text{duration of study drug exposure in days})]$. A study drug interruption on a given day is defined as an interruption of any study drug on that day.

Percentage of study drug compliance will be summarized based on the FAS, and presented by treatment groups. Percentage of study drug compliance will be summarized descriptively by the number of subjects (n), mean, SD, median, min, and max. It will also be summarized in categories: $<80\%$ and $\geq 80\%$ using frequency tables.

In addition, percentage of tablets taken will be calculated using the following formula: $100 \times [(\text{total number of tablets dispensed}) - (\text{total number of tablets returned})] / (\text{total number of tablets planned to be taken per day} \times \text{duration of study drug exposure in days})$. Summary similar to those for the study drug compliance will be produced based on the FAS. Due to discontinuation of the VX-561 25 mg qd and VX-561 50 mg qd treatment arms, the VX-561 25 mg tablet and its matching placebo were not dispensed following approval of Protocol v2.0; the calculations of drug compliance will not be conducted for the VX-561 25 mg tablet and its matching placebo.

8.2.7 Important Protocol Deviations

An important protocol deviation (IPD) is a deviation that may significantly affect the completeness, accuracy, or reliability of the study data or that may significantly affect a subject's rights, safety, or well-being. A blinded protocol deviation review team will categorize IPDs according to the protocol deviation plan.

IPDs (from the clinical database or from the site deviation log) will be provided in an individual subject data listing.

8.3 Efficacy and Pharmacodynamic Analyses

All efficacy and PD analyses described in this section will be based on the FAS, unless otherwise specified.

8.3.1 Analysis of Primary Efficacy Variable

8.3.1.1 Definition of Variables

The primary efficacy variable is the absolute change in ppFEV₁ from baseline at Week 12. Percent predicted FEV₁ is the ratio of FEV₁ (L) and predicted FEV₁ (L), expressed as a percentage. See [Appendix C](#) for more details

8.3.1.2 Primary Analysis

The primary efficacy endpoint is the absolute change in ppFEV₁ from baseline at Week 12. Per Protocol Version 2.0, the lower dose VX-561 arms (VX-561 25 mg qd and 50 mg qd) were discontinued. Most of the 17 subjects randomized to lower dose arms (VX-561 25 mg qd and 50

mg qd) did not complete study treatment. Due to the large proportion of missing assessments of lower dose arms, they are not included in MMRM analysis. The primary analysis (described below) is based on the within group mean of absolute change from baseline for VX-561 150 mg qd, VX-561 250 mg qd, and IVA 150 mg q12h treatment arms.

The primary analysis will be based on a mixed effects model for repeated measures (MMRM) using restricted maximum likelihood. The model will include the absolute change from baseline in ppFEV₁ at Day 15, Week 4, Week 8, and Week 12 from the current treatment arms (VX-561 150 mg qd, VX-561 250 mg qd, and IVA 150 mg q12h) as the dependent variable; treatment group, visit, and treatment by visit as fixed effects; with continuous baseline ppFEV₁ as covariates; and an unstructured covariance structure for the within-subject errors. If the model estimation does not converge, a compound symmetry covariance structure will be used. The efficacy data from the discontinued arms (VX-561 25 mg qd and VX-561 50 mg qd) will not be included in the model.

The primary results obtained from the model will be the within-group treatment effect estimate at Week 12 for each treatment arm. The adjusted mean with a 2-sided 95% CI will be presented in a table.

In addition, the adjusted mean and 95% CI of the treatment effect difference between each VX-561 arm and the IVA arm obtained from the MMRM model will be provided.

The ppFEV₁ values and absolute change from baseline values will be summarized descriptively (n, mean, SD, median, minimum and maximum) at each scheduled visit by treatment groups (in one table including IVA, VX-561 25 mg qd, VX-561 50 mg qd, VX-561 150 mg qd, VX-561 250 mg qd).

8.3.1.3 Sensitivity Analysis

No sensitivity analysis for the primary efficacy variable has been planned.

8.3.1.4 Subgroup Analysis

No subgroup analysis for the primary efficacy variable has been planned.

8.3.2 Analysis of Secondary Variable

8.3.2.1 Definition of Variables

[figure not shown]
Sweat chloride (SwCl): the SwCl value for a given visit will be calculated as the mean of the non-missing sweat chloride measurements obtained on the left and right arms at that visit. If one of the two arm measurements at a time point is missing, the other will be used as the mean. A volume ≥ 15 μL is required for an accurate determination of sweat chloride. Any results reported as having volume < 15 μL will be considered missing. Any sweat chloride values reported as < 10 mmol/L or > 160 mmol/L will be considered missing.

8.3.2.2 Analysis of Pharmacodynamics Variable: Sweat Chloride

The secondary endpoint is the absolute change from baseline in sweat chloride at Week 12 and will be analyzed similarly to ppFEV₁, including VX-561 150 mg qd, VX-561 250 mg qd, and IVA 150 mg q12h treatment arms only. The model will include treatment group, visit, and treatment by visit as fixed effects; with continuous baseline ppFEV₁ as covariates. Adjusted

means and 95% CIs of the average treatment effects at Week 12 will be obtained for within-group (for each arm) and between-group comparisons (between each VX-561 arm and the IVA arm).

In addition, the sweat chloride raw values and change from baseline values will be summarized descriptively and similar to ppFEV1 analysis.

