12.3.3.2 Pharmacodynamics: Sweat Chloride

The secondary endpoint is the absolute change from baseline in sweat chloride at Week 12 and will be analyzed similarly to ppFEV₁ for 250 mg qd VX-561, 150 mg qd VX-561, and IVA 150 mg q12h treatment arms. Adjusted means and 95% CIs of the average treatment effects at Week 12 will be obtained for within-group (for each arm) and between-group comparisons (between each VX-561 arm and the IVA arm). Details will be provided in the SAP.

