3 INTRODUCTION

This statistical analysis plan (SAP) for the final analysis is based on the approved clinical study protocol (CSP), Version 2.0, dated 03 Oct 2019, and most recent approved electronic case report form (eCRF), and approved eCRF completion guidelines.

This is a Phase 2, randomized, double-blind study to evaluate the efficacy and safety of VX-561 in subjects aged 18 years and older with cystic fibrosis.

The planned statistical analyses will contribute to evaluation of VX-561 doses based on totality of data, along with PK analysis and PK/PD analysis.

Per Protocol Version 2.0, the VX-561 25 mg qd and 50 mg qd treatment arms were discontinued ([REDACTED]). Most of the subjects randomized to the two dropped dose arms did not complete treatment. Therefore, the statistical analysis should be interpreted with caution.

This SAP (Methods) documents the planned statistical analyses of efficacy and safety endpoints for the final analysis.

The pharmacokinetic (PK) and pharmacodynamic (PD) characteristics of VX-561 will also be evaluated in the study. Selected analyses related to sweat chloride will be documented in this SAP, other PK and PD analyses will be documented separately in the clinical pharmacology analysis plan (CPAP) and the Modeling and Simulation Plan for the study.

This SAP (Methods) will be finalized and approved prior to data lock and treatment unblinding for the final analysis.

The Vertex Biometrics Department will perform the statistical analysis within the scope of the SAP. SAS® Version 9.4 or higher software (SAS Institute, Cary, North Carolina, USA) will be used to generate all statistical outputs (tables, figures, listings, and datasets).

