5.2 Secondary Endpoints

- Absolute change in sweat chloride concentrations from baseline at Week 12
- PK parameters of VX-561, IVA, and relevant metabolites
- Safety and tolerability, based on the assessment of adverse events (AEs), laboratory test results, standard 12-lead ECGs, vital signs, and pulse oximetry

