6.2 Sample Size and Power

The primary objective is to evaluate efficacy of VX-561. The primary efficacy endpoint is the absolute change in ppFEV1 from baseline at Week 12. Following discontinuation of the VX-561 25 mg qd and VX-561 50 mg qd treatment arms, the remaining subjects planned for enrollment will be randomized in a 2:2:1 ratio to the 3 current treatment arms. Assuming a within-group SD of 7 percentage points and a 10% dropout rate at Week 12: a sample size of 22 to 28 subjects in the VX-561 150, and 250 mg qd arms will provide a 95% CI of ± 3.4 to ± 2.9 percentage points around the observed mean absolute change in ppFEV1 from baseline at Week 12, based on 2 sided, 1-sample t statistics; a sample size of 11 to 14 subjects in the IVA 150 mg q12h arm will provide a 95% CI of ± 5.4 to ± 4.4 percentage points around the observed mean.

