6.3 Randomization

An interactive web response system (IWRS) will be used to assign subjects to treatment. A randomization list will be produced by Vertex Biostatistics or a qualified randomization vendor.

Subjects will be assigned a unique subject number. Only subjects who have completed screening assessments and are eligible for participation in the study will be randomized to receive study drug during the Treatment Period. Randomization will be stratified by ppFEV1 (<70 versus ≥70) determined during screening.

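### The sweat chloride model adjusts for baseline ppFEV1 but omits baseline sweat chloride, a loss of precision that one model term would recover

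*SAP*

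**What the plan says.** SAP 5.2 lists the endpoint as "Absolute change in sweat chloride concentrations from baseline at Week 12". SAP 8.3.2.2 states that it is handled like ppFEV1 and then gives the model: "The model will include treatment group, visit, and treatment by visit as fixed effects; with continuous baseline ppFEV₁ as covariates". It asks for adjusted means and 95% CIs at Week 12 within each arm, and for each VX-561 arm against IVA.

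The primary model in SAP 8.3.1.2 uses the same covariate phrase, "with continuous baseline ppFEV₁ as covariates". There it refers to the outcome's own baseline.

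Protocol 12.3.3.2 names no covariate: "The secondary endpoint is the absolute change from baseline in sweat chloride at Week 12 and will be analyzed similarly to ppFEV₁". It leaves details to the SAP, so SAP 8.3.2.2 governs. No other section adds baseline sweat chloride to the model, although SAP 8.2.2 tabulates it as a continuous baseline characteristic and Appendix A gives rules for deriving it.

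**The concern.** The section is at odds with itself. A model parallel to the ppFEV1 model would carry baseline sweat chloride, but the explicit sentence names another variable's baseline. The phrase was probably carried over from 8.3.1.2; that is an inference. A programmer following the sentence literally would leave the term out, while one following the instruction to treat the endpoint like ppFEV1 might put it in.

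Using a change score does not make the term redundant. Subtracting baseline fixes its slope at 1. With equal variances the best slope is the baseline-to-Week-12 correlation ρ, so the change still falls by (1 − ρ) mmol/L for each mmol/L of higher baseline. Baseline ppFEV1 removes this only so far as it predicts baseline sweat chloride. Nothing in the design balances baseline sweat chloride directly either: "Randomization will be stratified by ppFEV1 (<70 versus ≥70) determined during screening".

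At stake is the precision of the only pharmacodynamic endpoint, which the protocol's study rationale names among the data that may inform dose selection.

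**Working it through.** **Completers, from the plan's own figures.** The only precision figures in the documents are for ppFEV1 (protocol 12.1, SAP 6.2): SD 7, 10% dropout, one-sample t. With m = 0.9n rounded down and half-width t(0.975, m−1) × 7/√m:

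| Randomized n | Completers m | Recomputed | Stated |
|---|---|---|---|
| 22 | 19 | 3.37 | 3.4 |
| 28 | 25 | 2.89 | 2.9 |
| 11 | 9 | 5.38 | 5.4 |
| 14 | 12 | 4.45 | 4.4 |

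All four reproduce (the last is 4.448 before rounding). The calculations below use 25, 25 and 12 completers, 62 in total.

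**Assumptions.** Baseline and Week 12 sweat chloride have common SD s and correlation ρ between 0.3 and 0.9. Baseline ppFEV1 does not predict sweat chloride change. One visit with complete data stands in for the repeated-measures model.

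**Between arms.**
- Change score without its own baseline: variance 2s²(1 − ρ).
- With baseline sweat chloride added: residual variance s²(1 − ρ²).
- SE ratio: √[(1 − ρ²) / (2(1 − ρ))] = √[(1 + ρ)/2].
- Equivalent increase in sample size: 2/(1 + ρ) − 1.

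**Within arms.** The adjusted mean is evaluated at the pooled baseline mean, which is itself estimated. Its true variance is s²[(1 − ρ²)/n + (1 − ρ)²/62], against 2s²(1 − ρ)/n without the term.

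| ρ | Between-arm SE ratio | Equivalent extra subjects | Within-arm SD ratio, n = 25 | Within-arm SD ratio, n = 12 |
|---|---|---|---|---|
| 0.3 | 0.806 | 54% | 0.89 | 0.85 |
| 0.5 | 0.866 | 33% | 0.92 | 0.89 |
| 0.7 | 0.922 | 18% | 0.95 | 0.94 |
| 0.8 | 0.949 | 11% | 0.97 | 0.96 |
| 0.9 | 0.975 | 5% | 0.985 | 0.98 |

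**Simulation check.** In 4,000 runs per setting with 25/25/12 completers, the covariates were baseline ppFEV1 alone or ppFEV1 plus baseline sweat chloride. The baseline correlation between the two measures was set to 0 or −0.3. Between-arm CI half-width ratios were 0.81–0.83, 0.87–0.89, 0.93–0.94, 0.96 and 0.98–0.99 for the five values of ρ. Both models were unbiased, with between-arm coverage near 95%.

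**The same loss seen as chance imbalance.** A one-SE baseline difference between a VX-561 arm and IVA is √(1/25 + 1/12) = 0.351s. At the SAP's lower planned sizes it is √(1/19 + 1/9) = 0.405s. Without the term, the estimated contrast moves by (1 − ρ) times that difference. For 25 against 12 and s = 10 mmol/L (an illustrative value), this is 2.5, 1.8, 1.1, 0.7 or 0.35 mmol/L across the five values of ρ. As a fraction of the contrast's own SE it is √[(1 − ρ)/2] = 0.59, 0.50, 0.39, 0.32 or 0.22. Its square, (1 − ρ)/2, is exactly one minus the variance ratio (1 + ρ)/2, so this is not an additional effect.

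**Unequal variances.** If the Week 12 SD is k times the baseline SD, the variance ratio is k²(1 − ρ²)/(1 + k² − 2ρk). Over the same range of ρ, the SE ratio is 0.71–0.80 at k = 0.8 and 0.87 to almost 1.00 at k = 1.2. The gain disappears only when ρk = 1.

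**The case against.** The strongest reply is that the gain may be small. Subjects are on uninterrupted IVA before screening and then receive IVA or its deuterated form. The protocol expects a similar sweat chloride response at 150 mg, and each value averages the left- and right-arm collections where both are available. These features point to a high ρ without proving it, and at 0.8 to 0.9 with equal variances the between-arm narrowing is only 2.5% to 5%. If Week 12 values are more variable than baseline, it could be close to nil. This stands as a limit on size. It gives no reason to prefer ppFEV1 alone, and less variable Week 12 values would make the gain larger.

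A second point concerns the within-arm intervals. Once the term is added, the model-based CI treats the pooled baseline mean as fixed and becomes slightly too narrow. In simulation, coverage for a 25-subject arm fell to about 92–93% at ρ = 0.3 and 93–94% at 0.5, with little effect from 0.7 upward. This is true and should be known. It comes from evaluating means at the pooled baseline, a convention the primary model already uses, and the true within-arm sampling SD still falls.

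Third, the endpoint is secondary, is reported as estimates with CIs and no success threshold, and the separate exposure-response models do not depend on this covariate. That is also right. It makes this an inexpensive improvement, not a threat to the trial.

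**Conclusion.** The concern holds. The term is absent from the SAP's model, no other text supplies it, and the documents give no reason for adjusting by ppFEV1 alone. The consequence is lost efficiency and avoidable sensitivity to chance baseline differences; the between-arm contrast is neither biased nor miscovered. Under equal variances the between-arm CI would narrow by 2.5% to 19% for ρ from 0.9 down to 0.3, with smaller true gains within arms. Unequal variances could move this in either direction. The absence of the covariate is certain; the size of the gain rests on a correlation and an SD ratio that the documents do not give. The issue is worth correcting because it bears on the comparison with the smallest analyzed arm ("a sample size of 11 to 14 subjects in the IVA 150 mg q12h arm") and costs almost nothing to fix.

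**What to change.** In SAP 8.3.2.2, list two covariates: continuous baseline sweat chloride and continuous baseline ppFEV1. Keeping ppFEV1 retains an approximate adjustment for the screening stratum; it is not identical to the stratum, which rests on screening spirometry that may be post-bronchodilator.

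The cost is one SAP line, one model term and one degree of freedom. No data need to be collected and no subject is lost, since the change score already requires a baseline sweat chloride value. The slight narrowness of the within-arm CIs can be noted when they are reported.

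The change should be made while it still counts as pre-specified; SAP section 3 sets that point: "This SAP (Methods) will be finalized and approved prior to data lock and treatment unblinding for the final analysis".

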8.4 Safety Analysis

The overall safety profile of study drug will be assessed in terms of the following safety and tolerability endpoints:

- AEs
- Clinical laboratory values (hematology, serum chemistry, coagulation, and urinalysis)
- Standard 12-lead ECGs

- Vital signs
- Pulse oximetry

Safety endpoints will be analyzed based on the Safety Set. Only a descriptive analysis of safety will be performed.

All safety data from the TE period will be summarized by treatment groups (including IVA, VX-561 25 mg qd, VX-561 50 mg qd, VX-561 150 mg qd, and VX-561 250 mg qd).

8.4.1 Adverse Events

AEs will be classified as pretreatment AEs, treatment-emergent adverse events (TEAEs), or post-treatment AEs, defined as follows:

Pretreatment AE: any AE that started before the first dose date of study drug.

TEAE: any AE that worsened (either in severity or seriousness) or that was newly developed on or after the first dose date of study drug through the end of the TE Period.

Post-treatment AE: any AE that worsened or that was newly developed beyond the TE Period.

For AEs with completely missing or partially missing start dates, if there is no clear evidence that the AEs started before or after study treatment, the AEs will be classified as TEAEs during the Treatment Period.

Details for imputing missing or partial start dates of adverse events are described in [Appendix D](#).

An overview of all TEAEs will be summarized in the following categories and presented by treatment groups and VX-561 total:

- Number of TEAEs (total number of TEAEs only)
- Subjects with any TEAEs
- Subjects with TEAEs by strongest relationship
- Subjects with TEAEs by maximum severity
- Subjects with TEAEs leading to treatment discontinuation (discontinuation of any study drug)
- Subjects with Grade 3/4 TEAEs
- Subjects with related TEAEs
- Subjects with TEAEs leading to treatment interruption (interruption of any study drug)
- Subjects with serious TEAEs
- Subjects with related serious TEAEs
- Subjects with TEAE leading to death

The following summary tables of TEAEs will be presented by treatment groups:

- All TEAEs
- TEAEs by strongest relationship

- TEAEs by maximum severity
- TEAEs leading to treatment discontinuation
- TEAEs leading to treatment interruption
- Related TEAEs
- Serious TEAEs
- Related serious TEAEs
- TEAEs leading to death
- Grade 3/4 TEAEs

Summaries will be presented by MedDRA System Organ Class (SOC) and Preferred Term (PT) using frequency counts and percentages (i.e., number and percentage of subjects with an event). When summarizing the number and percentages of subjects, subjects with multiple occurrences of the same adverse event or a continuing adverse event will be counted once, and only the maximum severity level will be presented in the severity summaries, and the strongest relationship level in the relationship summaries.

All AEs, including pre-treatment AEs, TEAEs, and post-treatment AEs, will be presented in an individual subject data listing based on the All Subjects Set.

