6 STUDY DESIGN

6.1 Overall Design

This is a Phase 2 study of VX-561 monotherapy. A schematic of the study design is shown in Figure 6-1, which is randomized, double-blind, parallel-group, and active-controlled. The study was planned to evaluate 4 dose levels of VX-561 in subjects with CF who have a gating mutation and were previously taking a stable dose of IVA. Randomization will be stratified by ppFEV1 value at Screening (<70 versus ≥70). Per Protocol Version 2.0, the VX-561 25 mg qd and 50 mg qd treatment arms were discontinued ([REDACTED]); 44 subjects had been enrolled and randomized to the 5 treatment arms at that point. The remaining subjects planned to enroll will be randomized 2:2:1 to 3 treatment arms (VX-561 250 mg qd, VX-561 150 mg qd, and IVA 150 mg q12h).

Figure 6-1 VX18-561-101 Study Design

Screening 28 days	Treatment Period 12 weeks	Washout Period 3-5 days	Safety Follow-up 28 days after last dose
Enroll Subjects on Stable IVA Treatment	VX-561 250 mg qd	Washout VX-561 or IVA	Resume IVA
	VX-561 150 mg qd		
	VX-561 50 mg qd (treatment arm discontinued)		
	VX-561 25 mg qd (treatment arm discontinued)		
	IVA 150 mg q12h		

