8 STATISTICAL ANALYSIS

8.1 General Considerations

The Schedule of Assessments is provided in Section 3 of the protocol. The precision standards for reporting safety and efficacy variables are provided in an internal Biometrics document that specifies the programming rules including the precision for derived variables.

All individual subject data for those randomized or dosed with any amount of study drug will be presented in data listings.

Continuous variables will be summarized using the following descriptive summary statistics: the number of subjects (n), mean, SD, median, minimum value (min), and maximum value (max).

Categorical variables will be summarized using counts and percentages. Percentages will be presented to 1 decimal place.

Treatment-emergent (TE) period will include the time period starting from the date of the first dose of study drug to 28 days after the date of the last study drug taken in the treatment period, or the completion date of study participation, whichever comes earlier. The TE Period will be used for safety analyses unless specified otherwise.

Baseline value, unless otherwise specified, will be defined as the most recent non-missing measurement (scheduled or unscheduled) collected before the first dose of study drug. For ECG, baseline will be defined as the most recent non-missing pretreatment measurement (or the average of triplicate measurements, if the most recent non-missing pretreatment measurement is obtained in triplicate), before the first dose of study drug.

Absolute change from baseline will be calculated as postbaseline value – baseline value.

Relative change from baseline will be calculated as (postbaseline value – baseline value)/baseline value.

Unscheduled visits: Unscheduled visit measurements will be included in analysis as follows:

- In scheduled visit windows per specified visit windowing rules
- In the derivation of baseline and last on-treatment measurements
- In the derivation of maximum and minimum values during TE period, and maximum and minimum change from baseline values for safety analyses
- In individual subject data listings as appropriate

Visit windowing rules: The analysis visit windows for protocol-defined visits are provided in [Appendix A](#).

Incomplete/missing data will not be imputed, unless specified otherwise.

Outliers: No formal statistical analyses will be performed to detect or remedy the presence of statistical outliers, unless specified otherwise.

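### The TEAE tables set crude percentages for the truncated 25 mg and 50 mg arms beside full-length arms, and the visible SAP plans no patient-time rate

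*SAP*

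**What the plan says.** **What is tabulated.** SAP 8.4 states that "All safety data from the TE period will be summarized by treatment groups" and names all five arms, the two discontinued ones included. SAP 8.4.1 gives TEAE summaries "using frequency counts and percentages (i.e., number and percentage of subjects with an event". The TEAE overview also carries "Number of TEAEs (total number of TEAEs only" and is "presented by treatment groups and VX-561 total". SAP 8.2.1 defines that total as all VX-561 arms pooled.

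**How long subjects are observed.** Under SAP 8.1 the TE period runs from first dose "to 28 days after the date of the last study drug taken in the treatment period", or to the end of participation if that is earlier.

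**The truncation.** SAP 6.1 says "44 subjects had been enrolled and randomized to the 5 treatment arms at that point", that is, when the two low-dose arms were dropped. SAP section 3 says "Most of the subjects randomized to the two dropped dose arms did not complete treatment" and follows this with a general caution on interpretation. SAP 8.3.1.2 says of "Most of the 17 subjects randomized to lower dose arms" that they did not complete, and leaves those arms out of the primary model because so many assessments are missing.

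**What helps the reader.** SAP 8.2.5 tabulates exposure by arm, in days from first to last dose and in four-week categories. SAP 8.2.1 tabulates early discontinuation and its reasons by arm.

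**Use.** The statistical paragraph of the protocol synopsis says the safety analyses of all arms, discontinued ones included, are meant to support dose selection.

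Neither document shows a patient-time or time-to-event AE summary in its visible text. Both tables of contents have a blanked entry after the physical-examination item, so the absence can be stated for the visible text only.

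**The concern.** A percentage of subjects with an event depends on how long the subjects are watched. Here the watching time is tied to last dose, and two of the five columns hold mostly subjects whose dosing was cut short. The SAP recognizes the consequence for efficacy and removes those arms from the model, but makes no corresponding provision for the AE percentages.

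With the same underlying event rate in every arm, the 25 mg and 50 mg columns would show lower percentages than the 150 mg, 250 mg and IVA columns. The VX-561 total would be pulled down slightly relative to IVA. A reader comparing columns for dose selection could take part of that difference for better tolerability at low dose. The arm-level 150 mg, 250 mg and IVA percentages are not themselves distorted.

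**Working it through.** **Inputs from the documents.** Treatment lasts about 12 weeks (Protocol 9.1.2). The TE period adds up to 4 weeks (SAP 8.1). There are 17 low-dose subjects (SAP 8.3.1.2). Forty-four subjects were randomized 1:2:2:2:1 before the arms were dropped (Protocol 9.2). Planned sizes are 22 to 28 per remaining VX-561 arm and 11 to 14 on IVA (SAP 6.2).

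**Assumptions.** Stop times and TEAE incidence are not in the documents. I assume stops at weeks 2, 4 or 6, an incidence of 60% over a full TE period (40% and 80% as alternatives), and a constant hazard equal in all arms.

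**1. The plan's own count.** Expected low-dose subjects: 44 × 3/8 = 16.5, consistent with the stated 17. By arm: 44 × 1/8 = 5.5 on 25 mg and 44 × 2/8 = 11 on 50 mg, so about 6 and 11.

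**2. Follow-up.** A completer has about 12 + 4 = 16 TE weeks. A subject stopped at week t has about t + 4.

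**3. Shortfall for a subject who stops early.** λ = −ln(0.4)/16 = 0.0573 per week; expected incidence = 1 − exp(−λ(t + 4)).

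| Stop at week | TE weeks | Expected incidence | Shortfall from 60% |
|---|---|---|---|
| 2 | 6 | 29.1% | 30.9 points |
| 4 | 8 | 36.8% | 23.2 points |
| 6 | 10 | 43.6% | 16.4 points |

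For stops at week 2 and week 6, the shortfall is 22.6 and 12.7 points at 40% incidence, and 34.7 and 16.6 points at 80%. An arm's column moves by this amount only if everyone in it stopped then; otherwise by the stopped fraction of it.

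**4. VX-561 total.** All 17 stopped, 22 + 22 + 17 = 61 pooled: 17/61 × 30.9 = 8.6 points (week 2) and 17/61 × 16.4 = 4.6 points (week 6). Nine stopped (the fewest that is most of 17), 28 + 28 + 17 = 73 pooled: 9/73 × 30.9 = 3.8 and 9/73 × 16.4 = 2.0 points.

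**5. Sampling error.** SE = √[p(1 − p)(1/n₁ + 1/n₂)] at p = 0.60.
- 25 mg (6) against an arm of 28: √[0.24 × (1/6 + 1/28)] = 22.0 points; 1.96 SE = 43.2.
- 50 mg (11) against an arm of 28: √[0.24 × (1/11 + 1/28)] = 17.4 points; 1.96 SE = 34.2.
- VX-561 total against IVA: 14.3 points (73 v 14) to 16.0 points (61 v 11).

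No 60% scenario exceeds 1.96 SE in a column the SAP will show. The exception is at 80% incidence with every 50 mg subject stopped at week 2: 34.7 points against 1.96 × √[0.16 × (1/11 + 1/28)] = 1.96 × 14.2 = 27.9.

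**6. If events cluster early.** Put two thirds of the cumulative hazard in the first 4 weeks and spread the rest evenly over the next 12. A subject stopped at week 4 then accrues 2/3 + (1/3)(4/12) = 0.778 of it. The expected incidence is 1 − 0.4^0.778 = 51.0%, so the shortfall drops from 23.2 to 9.0 points. The same subject's event rate per TE week would be (0.778/8)/(1/16) = 1.56 times a completer's, with no dose effect.

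**7. Make-up of TE time.** The share after the last dose is 4/(t + 4) = 67%, 50% and 40% for stops at weeks 2, 4 and 6, against 4/16 = 25% for a completer.

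**8. Precision of a rate.** All 17 stopped at week 4: 17 × 8 = 136 patient-weeks and about 8 events at λ, or 5.9 per 100 patient-weeks (exact Poisson 95% CI 2.5 to 11.6). For about 6 subjects on 25 mg: 48 patient-weeks, about 3 events, 6.3 per 100 (1.3 to 18.3).

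**The case against.** The SAP does not hide the truncation. Section 3 states it and asks for caution, and disposition, exposure days and the total number of TEAEs are all planned by arm, so a reader can build a rough rate. That stands as mitigation. It is incomplete: the caution is general, the exposure table runs to last dose while AEs are counted to as much as 28 days later, and no AE table points to it.

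The shift is also hard to see in columns of about 6 and 11 subjects. That stands too, at 60% incidence. But sampling error falls in either direction, whereas this shift has one direction under equal constant rates.

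The remedy has its own faults, and these stand. A rate assumes a roughly constant hazard and is imprecise here. The intervals above also treat events as independent, although a count of all TEAEs includes repeats within a subject. In addition, Protocol 9.3.1 has subjects resume commercial IVA after the washout, and the documents do not fix when early stoppers resume. Post-dose TE time may therefore be largely IVA time, which is why a rate over TE time alone is not enough.

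A reader might infer that the laboratory, vital-sign and oximetry tables are understated by a calculable amount. The documents do not support a figure. It would need an independent, equal chance of an abnormal value at every test, which is doubtful for repeated values in one subject, and SAP 8.1 also admits unscheduled values. Only the qualitative remark holds: subjects who stop well before Week 12 have fewer scheduled tests.

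**Conclusion.** The point holds as a modest reporting weakness in the visible text. Percentages for arms with different follow-up stand side by side, with no patient-time measure and no pointer to exposure. Under equal constant rates, 60% incidence and stops at weeks 2 to 6, an early stopper's expected incidence is 16 to 31 points below a completer's, and the VX-561 total reads about 2 to 9 points low. These are scenarios, since stop times are not reported. Early clustering would shrink the shift, and a truly higher low-dose event rate could cancel or reverse it.

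A reader might go further and conclude that the low-dose percentages are wrong, or that a low dose will be favoured by mistake. Neither follows. The percentages correctly describe what was observed, safety is descriptive with no test or confidence interval affected, and nothing visible says that 25 mg or 50 mg remains a candidate dose.

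**What to change.** In SAP 8.4.1, keep every planned count and percentage, and:

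- Add supplementary exposure-adjusted TEAE rates by arm to the overview, All TEAEs and Serious TEAEs tables. Give TE-period events per 100 patient-weeks of TE time, and also events from first to last dose per 100 patient-weeks of that time, so that one version is free of post-dose IVA.
- Keep the VX-561 total as defined, and add a separately labelled VX-561 150 mg + 250 mg column to the AE overview.
- Footnote the AE tables to say that follow-up was shorter in the discontinued 25 mg and 50 mg arms, with a reference to the exposure table.
- State that the rates supplement the percentages and do not replace them, that they assume a roughly constant hazard, and that they count repeat events within a subject.

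The cost is programming and slightly longer tables; no new data are needed. The price in interpretation is that the rates will be imprecise and, if events cluster early, can read high in the truncated arms. If the sponsor judges them too imprecise to show, the footnote and the extra column are still worth having on their own.
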